### 9.2.2 Reactogenicity

Reactogenicity events are AEs that are common and known to occur following administration of this type of study vaccine. The following Toxicity Grading Scales will be used to grade solicited injection site and systemic (subjective and quantitative) reactions:

**Table 4: Injection Site Reactogenicity Grading**

Injection Site Reaction	Mild (Grade 1)	Moderate (Grade 2)	Severe (Grade 3)
Pain – experienced without touching the injection site (spontaneous discomfort)	Subject is aware of pain, but it does not interfere with daily activity, and if pain medication is used, it is Over the Counter (OTC) and used for less than 24 hours	Subject is aware of pain; there is interference with daily activity or OTC pain medication is used for more than 24 hours	Subject is aware of pain, and it prevents daily activity or pain requires prescription medication
Tenderness-experienced with touching the injection site	Subject is aware of pain, but it does not interfere with daily activity, and if pain medication is used, it is Over the Counter (OTC) and used for less than 24 hours	Subject is aware of pain; there is interference with daily activity or OTC pain medication is used for more than 24 hours	Subject is aware of pain, and it prevents daily activity or pain requires prescription medication
Pruritus	Does not interfere with daily activity	Interferes with daily activity	Prevents daily activity or requires prescription medication
Ecchymosis (Bruising)*	Does not interfere with daily activity	Interferes with daily activity	Prevents daily activity
Erythema (Redness)*	Does not interfere with daily activity	Interferes with daily activity	Prevents daily activity
Induration (Hardness)/Edema (Swelling)*	Does not interfere with daily activity	Interferes with daily activity	Prevents daily activity

\* Will also be measured in mm but size will not be used as halting criteria.

Ecchymosis, erythema and induration/edema as analyzed by measurement will be graded as follows:

**Table 5: Injection Site Reactogenicity Measurements**

Injection Site Reaction	Small	Medium	Large
Ecchymosis (Bruising)*	<20 mm	20 mm – 50 mm	>50 mm
Erythema (Redness)*	<20 mm	20 mm – 50 mm	>50 mm
Induration (Hardness)/Edema (Swelling)*	<20 mm	20 mm – 50 mm	>50 mm

\* Will not be used as halting criteria.

**Table 6: Subjective Systemic Reactogenicity Grading**

Systemic (Subjective)	Mild (Grade 1)	Moderate (Grade 2)	Severe (Grade 3)
Feverishness	No interference with daily activity	Some interference with daily activity	Significant interference, prevents daily activity
Fatigue	No interference with daily activity	Some interference with daily activity	Significant interference, prevents daily activity
Malaise	No interference with daily activity	Some interference with daily activity	Significant interference, prevents daily activity
Myalgia*	No interference with daily activity	Some interference with daily activity	Significant interference, prevents daily activity
Arthralgia*	No interference with daily activity	Some interference with daily activity	Significant interference, prevents daily activity
Headache	No interference with daily activity	Some interference with daily activity	Significant interference, prevents daily activity or headache requires prescription medication
Nausea	No interference with daily activity	Some interference with daily activity	Significant interference, prevents daily activity or nausea requires prescription medication

\* Not at injection site.

Oral temperature# will be graded as follows:

**Table 7: Quantitative Systemic (Oral Temperature) Reactogenicity Grading**

Systemic (Quantitative)	Mild (Grade 1)	Moderate (Grade 2)	Severe (Grade 3)
Fever* – oral †	38.0°C – 38.4°C 100.4°F – 101.1°F	38.5°C – 38.9°C 101.2°F – 102.0°F	>38.9°C >102.0°F

# Oral temperature assessed on Day 1 prior to the first study vaccination will be considered as baseline.

\* A fever can be considered not related to the study product if an alternative etiology can be documented.

† Subjects must not eat or drink anything hot or cold, or smoke within 10 minutes prior to taking oral temperature.

### 9.2.3 Additional Adverse Event Severity Grading

Pulse and BP# will be graded as follows:

**Table 8: Pulse and BP Adverse Event Grading**

Physiologic Parameter	Mild (Grade 1)	Moderate (Grade 2)	Severe (Grade 3)
Bradycardia – beats per minute	45 – 46	40 – 44	<40
Tachycardia – beats per minute	101 – 130	131 – 155	>155
Hypotension (systolic) mmHg	80 – 84	75 – 79	<75
Hypotension (diastolic) mmHg	50 – 54	45 – 49	<45
Hypertension (systolic) mmHg	141 – 155	156 – 160	>160
Hypertension (diastolic) mmHg	91 – 100	101 – 110	>110

# Pulse and BP assessed on Day 1 prior to the first study vaccination will be considered as baseline.

Clinical safety laboratory values# will be graded as follows:

**Table 9: Clinical Safety Laboratory Adverse Event Grading**

Hematology	Mild (Grade 1)	Moderate (Grade 2)	Severe (Grade 3)
WBC 10  /μL (Decrease)	2.50 – 3.90	1.50 – 2.49	<1.50
WBC 10  /μL (Increase)	10.60 – 15.00	15.01 – 20.00	>20.00

Hgb g/dL (Decrease) (Female)	10.1 – 11.4	8.5 – 10	<8.5
Hgb g/dL (Decrease) (Male)	11.0 – 12.4	9.5 – 10.9	<9.5
Platelets 10  /μL (Decrease) EDTA	125 – 139	100 – 124	<100
Platelets 10  /μL (Increase) EDTA	416 – 550	551– 750	>750
Platelets K/cu mm (Decrease) Citrate	115-124	100-114	<100
Platelets K/cu mm (Increase) Citrate	376-550	551-750	>750
Chemistry	Mild (Grade 1)	Moderate (Grade 2)	Severe (Grade 3)
ALT IU/L (Increase) (Female)	44 – 100	101 – 200	>200
ALT IU/L (Increase) (Male)	61 – 138	139 – 275	>275
Aspartate Amino Transferase IU/L (Increase) (Female)	37-90	91-180	> 180
Aspartate Amino Transferase IU/L (Increase) (Male)	44-108	109-215	> 215
Total Bilirubin mg/dL (Increase) – when accompanied by any increase in ALT	1.30 – 1.59	1.60 – 1.80	> 1.80
Total Bilirubin mg/dL (Increase) – when ALT is normal	1.30 – 1.89	1.90 – 2.40	> 2.40
Gamma-Glutamyl Transferase IU/L (Increase) (Female)	33-80	81-160	> 160
Gamma-Glutamyl Transferase IU/L (Increase) (Male)	50-123	124-245	> 245
Alkaline Phosphatase IU/L (Increase) (Female)	116-230	231-345	> 345
Alkaline Phosphatase IU/L (Increase) (Male)	116-230	231-345	> 345
Serum Amylase	122-182	183-242	>243
Serum Lipase	61-90	91-180	> 181
Creatinine mg/dL (Increase) (Female)	1.1 – 1.7	1.8 – 2.0	> 2.0
Creatinine mg/dL (Increase) (Male)	1.4 – 1.7	1.8 – 2.0	> 2.0

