**Table 1: Study Objectives and Outcome Measures**

Primary Safety Objectives	Primary Safety Outcome Measures

 
To assess the safety and reactogenicity of 2018/2019 Fluzone and Flublok with and without AF03 or Advax-CpG55.2 adjuvant.
 
	
 
Occurrence of solicited injection site and systemic reactogenicity events through approximately Day 8 after the first study vaccination.
 
Occurrence of unsolicited adverse events from the time of the first study vaccination through approximately Day 29.
 
Occurrence of all SAEs through approximately 12 months following receipt of the first study vaccination.
 
Occurrence of abnormal clinical safety laboratory AEs from the time of study vaccination through approximately Day 8 after the first study vaccination.
 

Primary Immunogenicity Objectives	Primary Immunogenicity Outcome Measures

 
To assess the serum hemagglutination inhibition (HAI) antibody responses against 2018/2019 QIV strains from baseline (Day 1) to approximately Day 29 after receipt of 2018/2019 Fluzone and Flublok with and without AF03 or Advax-CpG55.2 adjuvant.
 
	
 
The percentage of subjects achieving HAI titer seroconversion against the 2018/2019 QIV strains (defined as either a pre-vaccination titer <1:10 and a post-vaccination titer ≥1:40 or a pre-vaccination titer ≥1:10 and a minimum four-fold rise in post-vaccination antibody titer) on approximately Day 29 for each study group.
 
The percentage of subjects with an HAI titer ≥1:40 against the 2018/2019 QIV strains at baseline and approximately Day 29 for each study group.
 
Geometric mean titers (GMTs) of serum HAI against the 2018/2019 QIV strains at baseline and approximately Day 29 for each study group.
 

	
 
• Ratio of GMTs of serum HAI against the 2018/2019 QIV strains between adjuvanted and unadjuvanted study groups at baseline and approximately Day 29.
 
• Geometric mean fold rise (GMFR) in HAI titers from baseline (Day 1) against the 2018/2019 QIV strains at approximately Day 29 for each study group
 

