### **7.2.1 Clinical Laboratory Evaluations**

Urine or serum pregnancy tests will be performed locally by the site at the screening visit (optional) and within 24 hours prior to first study vaccination for all women of childbearing potential. Results must be negative and known prior to randomization on Day 1 and administration of first study vaccination to be eligible for participation in this trial and receipt of study vaccination.

The ESR evaluation will be performed locally by the site at the screening visit and confirmed as less than 30 mm per hour to be eligible for participation in this trial and receipt of the first study vaccination.

Clinical safety laboratory parameters (WBC, Hgb, PLT, ALT, AST, GGT, ALP, Bilirubin (total), serum lipase and serum amylase and Cr) will be collected at the screening study visit and will be sent to the Central Clinical Laboratory. The results from the clinical safety laboratory parameters collected at the screening visit must be reviewed prior to the first study vaccination and must be

within acceptable ranges to be eligible for receipt of the first study vaccination (see [Section 5.1.1](#)). The safety laboratories will be repeated prior to receipt of the first study vaccination. However, the results from the clinical safety laboratory parameters collected prior to the study vaccination will not be available or reviewed prior to the study vaccination. Clinical safety laboratory parameters collected immediately prior to the first study vaccination will serve as the baseline and will be repeated on approximately Day 8.

The volume of venous blood to be collected for ESR and clinical safety laboratory evaluations is presented in [Table 3](#).

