### **9.2.5 Procedures to be Followed in the Event of Abnormal Laboratory Test Values or Abnormal Clinical Findings**

The site PI or appropriate sub-investigator is responsible for recording all AE/SAEs that are observed or reported during this trial, regardless of relationship to study product. AE/SAEs, abnormal laboratory test values or abnormal clinical findings will be collected, assessed, documented, reported, and followed appropriately, using a local laboratory as necessary. In determining eligibility, refer to [Section 5.1](#) and the protocol-specific MOP.

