### 9.5.1 Halting Rules for the Sentinel Subjects

- Any subject experiences ulceration, abscess or necrosis at the injection site.
- Any subject experiences laryngospasm, bronchospasm or anaphylaxis within 24 hours after administration.
- Any subject experiences generalized urticaria (defined as occurring at more than two body parts) within 72 hours after administration of study product.
- Any subject experiences an SAE (except for accident or trauma) after administration of the study product.
- Any subject experiences acute weakness of limbs and/or cranial nerve innervated muscles (description of potential signal of GBS) after administration of study product.
- Any subject that experiences grade 3 AE including lab, local or systemic solicited reactogenicity events (excluding measured grades of erythema and induration alone)

- Two or more subjects experience the same grade 2 (same HLG by MedDRA coding) AE including local or systemic solicited reactogenicity events (excluding measured grades of erythema and induration alone)

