### 9.5.2 Halting for Study

Additional enrollment and study interventions/administration of study products in this trial will be halted for DSMB review/recommendation if any of the following are reported after the first study vaccination:

- Any subject experiences ulceration, abscess or necrosis at the injection site that is considered related to study product administration.
- Any subject experience laryngospasm, bronchospasm or anaphylaxis within 24 hours after administration of study product that is considered related to study product.
- Two or more subjects experience generalized urticaria (defined as occurring at more than two body parts) within 72 hours after administration of study product that is considered related to study product.
- Any subject experiences an SAE after administration of study product that is considered related to study product.
- Any subject experiences acute weakness of limbs and/or cranial nerve innervated muscles (description of potential signal of GBS) after administration of study product.
- Any subject develops a PIMMC after administration of study product.
- 10% of subjects (minimum 3 subjects) experience a grade 3 injection site or systemic solicited adverse event (excluding measured grades of erythema and induration alone).
- 10% of subjects (minimum 3 subjects) experience same grade 3 AE (unsolicited and laboratory abnormality), in the same HLG by MedDRA coding, considered related to study product.

Grading scales for solicited injection site and systemic (subjective and quantitative) reactions are included in [Section 9.2.2](#).

Grading scales for clinical safety laboratory AEs are included in [Section 9.2.3](#).

If any of the halting rules are met following any subject receipt of study vaccination, then this trial will not continue with the remaining enrollments or study vaccinations without a review by and recommendation from the DSMB to proceed.

DMID retains the authority to suspend additional enrollment and study interventions/administration of study products during this trial, as applicable.

The DMID Medical Monitor is empowered to stop enrollment and study vaccinations if AEs that meet the halting criteria are reported.

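### Serum amylase 243 and serum lipase 181 have no severity grade, at the Grade 3 boundary that the halting rules use

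*Protocol*

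**What the plan says.** Protocol Table 9 sets three severity bands for each safety laboratory parameter. The two rows at issue read "Serum Amylase 122-182 183-242 >243" and "Serum Lipase 61-90 91-180 > 181". SAP Table 10 carries the same cut-points. The vital-sign rows in Protocol Table 8 use the same layout, for example "Hypertension (systolic) mmHg 141 – 155 156 – 160 >160".

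The grades are used in three places:

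- **Primary safety outcome (Protocol Table 1):** "Occurrence of abnormal clinical safety laboratory AEs from the time of study vaccination through approximately Day 8".
- **Sentinel halting rule (Section 9.5.1):** "Any subject that experiences grade 3 AE including lab, local or systemic solicited reactogenicity events". One such event is enough, and relatedness is not required.
- **Study-wide halting rule (Section 9.5.2):** "10% of subjects (minimum 3 subjects) experience same grade 3 AE (unsolicited and laboratory abnormality", in the same MedDRA grouping and considered related to study product. That section refers to Section 9.2.3 for the laboratory grading scale.

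On sampling, Section 7.2.1 states that the pre-vaccination safety laboratory values "will serve as the baseline and will be repeated on approximately Day 8".

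**The concern.** A grading scale should give every abnormal value exactly one grade. Here one value of each analyte has none, and the gap lies at the cut-point that separates Grade 2 from a halting-level event. Read literally, a sentinel subject with lipase 181 does not meet the Grade 3 halting rule and is not Grade 2 either.

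The gap also reaches the planned outputs. The SAP laboratory severity tables (Tables 148 and 149 for these analytes) allow only None, Grades 1 to 3, or Missing. An ungraded abnormal value programmed literally could be counted under None. SAP Section 9.6 limits the abnormal-result listings to Grade 1 or higher, so Table 162 could omit it.

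**Working it through.** No sample size, power or error rate is involved. The check asks whether each grade starts where the previous one stops.

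**Inputs.** The 22 rows of Protocol Table 9 (17 graded upward, 5 downward), the 6 rows of Protocol Table 8, and the amylase and lipase rows of SAP Table 10.

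**Test for an upward row.** The bands meet if the Grade 3 threshold *t* (Grade 3 is > *t*) equals the Grade 2 maximum *m*. If *t* > *m*, values above *m* up to and including *t* have no grade.

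| Row | Grade 2 | Grade 3 | *t* − *m* | Ungraded whole numbers |
|---|---|---|---|---|
| AST, female | 91–180 | >180 | 0 | none |
| ALP | 231–345 | >345 | 0 | none |
| Amylase | 183–242 | >243 | 243 − 242 = 1 | 243 |
| Lipase | 91–180 | >181 | 181 − 180 = 1 | 181 |

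Lipase and female AST share the Grade 2 band 91–180, yet one continues at >181 and the other at >180.

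**Enumeration.** Listing every integer from the Grade 1 lower limit upward for ALT, AST, GGT, ALP, amylase, lipase and both platelet-increase rows gave only two ungraded values: amylase 243 and lipase 181.

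**Row count at the Grade 2/Grade 3 boundary.**

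- Table 9, upward: 15 of 17 meet.
- Table 9, downward: 5 of 5 meet.
- Table 8: 6 of 6 meet.
- Total: 15 + 5 + 6 = 26 of 28. The exceptions are amylase and lipase.

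At the Grade 1/Grade 2 boundary all 28 rows meet at the printed precision, including amylase (182, then 183) and lipase (90, then 91). This points to a slip in two cells rather than an intended gap.

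**Exposure.** With one scheduled post-vaccination draw at Day 8, there are at most 6 sentinel results and 240 results overall per analyte. For the two analytes together that is 2 × 6 = 12 and 2 × 240 = 480. Early-termination and unscheduled draws could add a few.

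**After the change.** With Grade 3 set at >242 and >180, the same enumeration leaves no ungraded integer in either row.

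**The case against.** The strongest objection is that the consequence is close to nil. Subjects enter with amylase no higher than 121 and lipase no higher than 60 (Section 5.1.1). Measured from those limits, a result would have to rise about twofold (243/121 ≈ 2.0) or threefold (181/60 ≈ 3.0) by Day 8 and land on one exact integer. A sensible reader would probably treat 243 and 181 as the first Grade 3 values. No estimate or confidence interval for immunogenicity depends on them.

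There are also backstops. Section 9.2.5 requires that "abnormal laboratory test values or abnormal clinical findings will be collected, assessed, documented, reported, and followed appropriately", whatever the grade. SAP Listing 23 shows every chemistry result. Under Section 9.5.2 the sponsor may suspend enrollment at its discretion, and the study-wide rule also needs relatedness and 10% of subjects with a minimum of 3. All of this stands, and it keeps the point minor. The relatedness and 10% conditions do not apply to the sentinel rule, however, where one Grade 3 result is enough.

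It can also be argued that Section 9.2.1 fills the gap, since it gives general mild, moderate and severe definitions for a study physician to apply. Those definitions are for events outside the protocol's grading system. Amylase and lipase are inside it, so the fallback does not clearly apply, and nothing else in the documents assigns a grade to these values.

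**Conclusion.** The gap is real in both documents: amylase 243 and lipase 181 have no grade. It is a minor correction. The size assumes whole-number results, as the printed cut-points and eligibility limits suggest. Few results, possibly none, will be affected, and safety conclusions are not at risk from it. It is still worth correcting, because it leaves sites and programmers to make an ad hoc decision at a threshold that can halt the study.

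**What to change.** In Protocol Table 9 and SAP Table 10, set amylase Grade 3 to >242 and lipase Grade 3 to >180. This matches the form of the other upward-graded rows. It is also safer than ≥243 and ≥181, which would close the gap only for whole-number results.

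The cost is two cells in each document, four in total, with no change to data collection. Section 14.2 requires IRB approval of protocol amendments before they are implemented, so the protocol cells can reasonably wait for the next amendment. If Day 8 results are already available, a search of the chemistry data for amylase 243 and lipase 181 will show whether any subject is affected.

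As a separate query, not a claimed error: ask the sponsor whether the citrate platelet eligibility upper limit (325, Section 5.1.1) and the start of the Grade 1 increase (376, Table 9) are meant to differ. An eligibility limit and a grading limit need not coincide.

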# Clinical safety laboratory evaluations assessed on Day 1 prior to the first study vaccination will be considered as baseline.

#### 9.2.4 Serious Adverse Events

**Serious Adverse Event (SAE):** An AE or suspected adverse reaction is considered “serious” if, in the view of either the site PI (or appropriate sub-investigator) or sponsor, it results in any of the following outcomes:

- Death,
- A life-threatening AE\*,
- Inpatient hospitalization or prolongation of existing hospitalization,
- A persistent or significant incapacity or substantial disruption of the ability to conduct normal life functions, or
- A congenital anomaly/birth defect.
- Important medical events that may not result in death, be life-threatening, or require hospitalizations may be considered serious when, based upon appropriate medical judgment they may jeopardize the patient or subject and may require medical or surgical intervention to prevent one of the outcomes listed in this definition. Examples of such medical events include allergic bronchospasm requiring intensive treatment in an emergency room or at home, blood dyscrasias or convulsions that do not result in inpatient hospitalization, or the development of drug dependency or drug abuse.

\* Life-threatening AE. An AE is considered “life-threatening” if, in the view of either the site PI (or appropriate sub-investigator) or sponsor, its occurrence places the patient or subject at immediate risk of death. It does not include an AE that, had it occurred in a more severe form, might have caused death.

SAEs will be:

- Assessed for severity and relationship to study product or alternate etiology (if not related to study product) by a licensed study physician listed on the Form FDA 1572 as the site PI or sub-investigator.
- Recorded on the appropriate SAE form and entered into the eCRF.
- Followed through resolution by a licensed study physician listed on the Form FDA 1572 as the site PI or sub-investigator.

- Reviewed and evaluated by the DSMB (periodic review unless related), DMID, and IRB.

### **9.2.5 Procedures to be Followed in the Event of Abnormal Laboratory Test Values or Abnormal Clinical Findings**

The site PI or appropriate sub-investigator is responsible for recording all AE/SAEs that are observed or reported during this trial, regardless of relationship to study product. AE/SAEs, abnormal laboratory test values or abnormal clinical findings will be collected, assessed, documented, reported, and followed appropriately, using a local laboratory as necessary. In determining eligibility, refer to [Section 5.1](#) and the protocol-specific MOP.

## **9.3 Reporting Procedures**

Solicited injection site and systemic reactogenicity events will be documented and reported from the time of the first study vaccination through 7 days after the first study vaccination.

Clinical safety laboratory AEs will be documented and reported from the time of the first study vaccination through approximately 7 days after the first study vaccination.

Unsolicited non-serious AEs will be documented and reported from the time of the first study vaccination through approximately Day29.

SAEs and AESIs (including Protocol Specified AESIs, MAAEs, NOCMCs and PIMMCs) will be documented and reported from the time of the first study vaccination through approximately 12 months after the first study vaccination.

